Patients will be recruited from the inpatient services and outpatient clinics of the University of Oklahoma Health Sciences Center. A meeting with all study personnel to review the study protocol will be held before initiation of the study, as well as every 3-6 months, depending on study progress. Informed consent will be obtained prior to enrollment in the study. The randomization schedule will be implemented with the use of concealed envelopes and it will be stratified by sex. Blocked randomization will be used to decrease the chance of imbalances in the two groups over time.

After informed consent and screening procedures are completed, all patients will undergo noninvasive continuous ECG monitoring for 2 weeks to evaluate their AF burden (the percent of time spent in AF) using an adhesive waterproof continuous monitoring patch (Zio[®] Patch). The Zio[®] Patch (iRhythm Technologies, Inc) is an FDA approved, single-lead, lightweight, 14-day ambulatory ECG adhesive patch monitor. The patch is well tolerated and allows significantly longer continuous monitoring than a regular Holter monitor, leading to an improved AF detection rate ³⁴. After the 2-week monitoring period, patients will be randomly assigned (1:1) to active or sham LLTS. Patients will be blinded to the treatment allocation, and every effort will be made to conceal from the study personnel the nature of the intervention in each study arm. Blinding of the patients will be accomplished by having a sham control arm, in which stimulation will be delivered to a different site (the ear lobe), devoid of vagal innervation ³⁵. By doing so, all patients will be aware that they are receiving stimulation, but they will not be told which site achieves active VN

stimulation. The patients will be requested to refrain from discussing the details of their treatment with other patients in the clinic and with the physicians, nurses and the rest of clinic staff. The clinical coordinator and a clinic physician who will not participate in any of the other study related assessments will be unblinded to the treatment allocation and will instruct the patients on the proper use of the device. These study personnel will be designated to address the patients' questions and concerns as well as to record any side effects related to the use of the device.

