Active LLTS will be performed by use of a transcutaneous vagus nerve stimulation (tVNS) device with electrodes attached to the tragus of the ear, which is innervated by auricular branch of the vagus nerve ³⁵.

The Parasym targeted transcutaneous vagus nerve stimulation (tVNS) device (Parasym Ltd) will be used for LLTS or sham stimulation. The device will be connected to a clip electrode that will be attached to the external ear. In the active group, the ear clip electrode will be attached to tragus in the active stimulation group (Figure 3). The ear (tVNS) device has not been previously reviewed by the FDA for experimental studies. It has been however studied in Europe and is available in the European market under the name Parasym ®. The same LLTS protocol will be followed in sham LLTS arm, but the electrode will be placed on the ear lobe, which is devoid of vagus innervation 35. The LLTS unit will be set at a pulse width of 200 µs

[figure not shown]
Figure 3. Position of the electrode clip used for active stimulation on the tragus.

and a pulse frequency of 20 Hz. Amplitude will be titrated to the level of sensory threshold, typically in the range of 10-50 mA. The stimulation strength will be gradually increased until the patient experiences mild discomfort, then decreased by 1 mA below that threshold. LLTS will be applied continuously for 1 hour daily. After individual training, participants will apply LLTS by themselves as part of their daily routine. Participants will be requested to keep a daily log with the time and duration of LLTS application, amplitude settings and any comments related to each daily session to monitor adherence. Patients and investigators will be blinded to the treatment allocation. Blinding of the patients will be accomplished by having a sham control arm, in which stimulation will be delivered to a different site (the ear lobe), devoid of vagal innervation ³⁵. Thus, all patients will be aware that they are receiving stimulation, but they will not be told which site achieves active stimulation. The clinical coordinator will be unblinded to treatment allocation and will instruct the patients on the proper use of the device. In patients with pacemakers, the pacemaker will be

tested with the LLTS unit to assess for interaction. In case of interaction (the stimulation artifact of the LLTS unit picked up by the pacemaker), the patients will be excluded from the study.

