We will provide formal training to the patients on how to use the tVNS device, how to place the electrode pads and apply simulation. During the baseline visit all patients will be asked to repeat the process themselves under direct supervision, to ensure correct use of the device. The clinical coordinator will contact the patients once a week to ensure proper use of the device and assist with battery replacement, if needed. Blood draw will be done using standard sterile techniques is not associated with more than minimal risk. The blood samples will be processed and stored in the Immunology Lab at BRC. The samples will be de-identified before processing and the technician performing the processing will only have access to de-identified data.

a. Address measures instituted to protect the privacy and/or confidentiality of participant PHI (locking cabinets for participant records containing PHI, use of password protected programs, limited access to PHI, etc.).

[figure not shown]
The patient charts will be obtained after informed consent. A representative data sheet will be constructed and approved for confidentiality. Names will be replaced by numbers and the subject's code and name will be kept in separate repositories.

6. Describe potential benefits and importance to the participants and others.

Catheter ablation, with the poor long-term success rate and high cost, is not likely to be the mainstay therapy for a large population of patients with drug-refractory AF. The development of alternative non-invasive therapies is essential for the management of patients with AF. If this therapy proves to be effective in suppressing AF and AF-related inflammation, both study participants and others may benefit from this non-invasive treatment option with less risk involved. The results of this study may form the basis for a larger clinical trial to further investigate the utility of LLTS in humans.

7. Discuss why risks are reasonable in relation to benefits.

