AF is the most common cardiac arrhythmia, affecting more than 10 million Americans, and is associated with significant morbidity and mortality. Current therapies for AF (medications and catheter ablation) are limited by suboptimal efficacy and potential toxicity. In this study, we hypothesize that intermittent (1 h daily) LLTS, an alternative non-invasive approach, for 6 months will suppress inflammatory cytokines and decrease AF burden in patients with paroxysmal AF. These investigations will establish the first evidence of the long-term effects of LLTS on suppression of inflammation and AF in patients with paroxysmal AF and may provide the basis for a potential expansion of the therapeutic targets of this treatment modality beyond AF, into other inflammatory conditions. Importantly, in light of the increasing number of patients with AF and

the poor success and potential side effects of the currently available treatment options, an alternative approach such as the one tested in this study (tragus stimulation) may benefit a large number of patients in Oklahoma.

H. Data and Safety Monitoring Plan

1. Describe the Data and Safety Monitoring Plan (DSMP)

An independent Data Safety Monitoring Board (DSMB) committee consisting of 2 cardiologists and 1 statistician will monitor the study. All adverse events will be reported to the DSMB committee. The committee will review recruitment and retention data, protocol adherence data, data quality, and safety data every 6 months

a. reporting mechanisms for adverse events to the IRB, FDA, and NIH

Clinical staff will track from patient report, physical assessments and documentation of clinical emergencies, adverse events according to federally published grading (0=no adverse event; 1=mild; 2=moderate; 3=severe and undesirable adverse events; 4=life threatening/disabling; or 5=death) and attribution (1=unrelated; 2=unlikely; 3=possible; 4=probable; 5=definite) scales. Clinical staff will report findings to the Investigator, who will then advise the IRB, NIH and FDA as indicated. Given the mild risk nature of the study, composite reports will be reviewed every ten patients to assure that untoward events do not occur systematically, and dropout cases will be reviewed singly to learn whether further inquiry or modifications should be made to improve study implementation.

b. adverse event (AE) grading

0=no AE; 1=mild; 2=moderate; 3=severe and undesirable AE; 4=life threatening/disabling; or 5=death

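### Device-related side effects are recorded by staff who know the arm, and this route is not reconciled with the adverse event process in Section H

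*Combined protocol and SAP*

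**What the plan says.** **Who is unblinded.** Section D, Specific Aim 1, on knowledge of the allocation: "The clinical coordinator and a clinic physician who will not participate in any of the other study related assessments will be unblinded to the treatment". The same section says: "Patients and investigators will be blinded to the treatment allocation".

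**What the unblinded staff record.** The next sentences of Section D give these two people the job of handling patients' questions "as well as to record any side effects related to the use of the device".

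**What patients are asked not to discuss.** Also in Section D, patients receive this request: "refrain from discussing the details of their treatment with other patients in the clinic and with the physicians, nurses and the rest of clinic staff".

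**Weekly contact.** Section G, item 5: "The clinical coordinator will contact the patients once a week to ensure proper use of the device". Help with batteries is the other stated purpose. No question about symptoms or adverse events is mentioned.

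**The general adverse event process.** Section H, item 1a: "Clinical staff will track from patient report, physical assessments and documentation of clinical emergencies". Events are graded from 0 to 5 and attributed on a scale from 1 (unrelated) to 5 (definite). The clinical staff report to the investigator, who informs the IRB, NIH and FDA as indicated. Section H, item 1 sends all adverse events to the DSMB.

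**Follow-up visits.** Section D has a history, an examination and recording of cardiovascular events at 1, 3 and 6 months. It does not say who records them or whether that person is blinded.

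**The concern.** Attribution is the safety judgement most easily influenced by knowing the allocation. Section G, item 3 lists dizziness, mild dyspnea and headaches among the known effects of this kind of stimulation. A patient with AF could report any of these in either arm. If the person deciding whether to record such a complaint as a device effect knows which ear site is stimulated, the threshold for calling it device-related may differ between arms, in either direction and without intent.

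The protocol calls the trial double-blind without excepting safety. It also says that the device has not previously been reviewed by the FDA for experimental studies, so the safety record from this trial carries weight. A reader of the results would want to know whether relatedness was judged blind. The plan does not settle that.

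**Working it through.** The plan gives no figure on this point, and its sample size calculation does not bear on it. The check is to set the provisions side by side.

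| Step | Section D route | Section H route |
|---|---|---|
| Who | Coordinator and one physician | Clinical staff, not further defined |
| Blinded? | No, stated | Not stated |
| Which events | Side effects related to the device | Adverse events, including unrelated ones |
| Relatedness judged | On deciding what falls within the remit | On a five-point scale |
| Passed on to | Not stated | Investigator; DSMB receives all adverse events |

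1. **The relatedness judgement.** The Section D remit is defined by relatedness. To apply it, the recorder must first decide whether a complaint comes from the device, and both recorders know the arm. This follows from the text alone.

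2. **Are the two groups the same people?** Section D says that the unblinded physician takes no part in other study assessments, which suggests separation. It does not mention adverse event grading, and Section H does not mention blinding. Both readings leave a difficulty:
   - If they are the same people, grading and attribution under Section H are also unblinded.
   - If they are different people, nothing says how a complaint made to the coordinator enters the Section H record. The patient has also been asked not to discuss treatment details with the rest of the clinic staff. A complaint of dizziness during a session is hard to describe without mentioning the session.

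3. **The contacts.** The most frequent planned contact is weekly, with the unblinded coordinator, and its stated purposes concern the device. The 1-month interview is also held by unblinded staff and covers problems with home use and adherence. Neither has a stated adverse event question.

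4. **Who could judge blind.** Section D already describes the investigators as blinded, and Section H already sends findings to the investigator. But Section H has the clinical staff apply the grading and attribution scales before that step.

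5. **Sensitivity.** The documents give no adverse event rates, so no bias can be calculated. The arms are small, however. With 52 patients allocated 1:1, each arm has 26, and counting or not counting one patient as having a device-related effect moves that arm's percentage by 1/26 = 3.8 points. This shows how much one judgement weighs. It does not estimate how many are wrong.

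**The case against.** The strongest reply is that the plan captures more than the Section D sentence suggests. Section H draws on patient report, physical assessment and emergency records. Its scale includes unrelated events, and all adverse events go to the DSMB. It adds composite reports every ten patients and individual review of dropouts. The follow-up visits record cardiovascular events whatever their cause. Patients, who are blinded, also keep a daily log with comments on each session. All of this stands, although the log's stated purpose is adherence and no path from it to the adverse event record is described.

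Three stronger readings are tempting, and the documents support none of them.

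- A reader might infer that unblinded staff record nothing but device-related effects, so that adverse events in general are filtered or fail to reach the DSMB. Section D does not make that remit exclusive, and Section H provides wider capture.
- A reader might infer that patients are told not to report symptoms. The request concerns details of treatment, in a paragraph about blinding, and symptoms are not mentioned. At most it could be misread.
- A reader might compare the number of weekly contacts with the three visits and conclude that most safety data are collected unblinded. That counts contacts, not events lost or misjudged, and the weekly contact is not described as a safety contact at all.

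Two further replies have force. Section E lists no safety outcome and no between-arm safety comparison, so no planned test is compromised; the issue is the quality of the safety record. Sending device complaints to unblinded staff also has a good purpose: redness or pressure marks would show a blinded investigator which site was stimulated. That justifies the arrangement for local reactions. It does not justify it for dizziness, dyspnea or headache, which do not reveal the site.

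**Conclusion.** The point holds in a limited form. Section D assigns the first judgement of device-relatedness to people who know the arm. Section H describes a second process in which blinding is unstated, and the plan does not connect the two. The wording of the discussion request and the absence of an adverse event question at the weekly contact add avoidable ambiguity.

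The effect is on the credibility of adverse event attribution. It cannot be quantified from the documents, and neither its direction nor its presence is established. The primary outcome, AF burden from the patch monitor, is unaffected. The conclusion assumes that recording only what is related requires a judgement of relatedness, and that no separate manual outside these documents assigns the grading to blinded staff. The plan should be amended, because it already has a blinded assessor and enough patient contacts to resolve the matter.

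**What to change.** - **Section D, recording.** Have the unblinded staff record every untoward event, whatever its perceived relation to the device. They should ask the same open question in both arms at each weekly contact and visit, and pass each record into the Section H process with the stimulation site masked.
- **Section H, assessment.** State that a blinded investigator assigns grade and attribution. Say who the clinical staff are and whether they are blinded.
- **Section D, discussion request.** Add that it does not cover symptoms, which patients may report to any member of staff.
- **Local reactions.** Keep reactions at the ear site with the unblinded physician and tabulate them separately, so that they do not reveal the arm.
- **Section G, item 5.** Add the open question to the stated purposes of the weekly contact.

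The cost is protocol wording and a short contact form, with no new staff or visits. The drawbacks are that more trivial events will be recorded and that a description may occasionally reveal the site. Masking and the separate handling of local reactions keep that risk small.

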Patients will be anticoagulated according to the 2014 ACC/AHA guidelines ³⁶. Specifically, patients with a CHADS2-VASc score of 1 or greater will receive anticoagulation, with either one of the new oral anticoagulants or warfarin (target INR 2-3). All other medications, including antiarrhythmic medications will be continued. The choice of antiarrhythmic medications will be left at the discretion of the treating physician. The experimental device will be used in addition to all the other medications; in other words, the device will be used only with individuals continuing drug treatment.

Patients will be enrolled in the study over 17 months and the total duration of the study will be 24 months (each patient will be followed for 7 months). During the baseline visit (after the 2 week monitoring period), a complete history and physical examination will be done by one of the investigators. Laboratory data and echocardiographic data, when available, will also be reviewed. A 5-minute ECG for HRV analysis (see below) will be performed at the same time. After the ECG is completed, 10ml of blood will be drawn for cytokine analysis (see below). Since blood draw is likely to cause an increase in the sympathetic tone, it will be performed after the ECG is completed, to avoid any interfering with HRV analysis. After the ECG and blood draw is completed (to avoid

contamination of the baseline data by stimulation), patients will be instructed on how to use the LLTS and attach the electrode pads and will be asked to repeat the process themselves under direct supervision, to ensure correct use of the device. This process will be done by a clinical coordinator and/or physician who is unblinded to random allocation.

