We intend to recruit 52 patients. Participants will be evaluated at 1, 3 and 6 months. At each follow-up visit, patients will have a brief history and physical examination, and any cardiovascular events, including symptomatic AF episodes will be recorded. In addition, the discomfort threshold for tragus stimulation will be obtained to ensure that patients are receiving adequate stimulation. At the 1 month visit, the patients will be interviewed by the unblinded physician or clinical coordinator to address any issues with LLTS administration at home, and to assess their adherence to the stimulation protocol. At the 3 and 6 month visit, patients will have a 5-minute ECG and blood drawn, as during the baseline visit. In addition, patients will undergo noninvasive continuous ECG monitoring for 2 weeks to evaluate their AF burden using an adhesive patch (Zio[®] Patch).

A schematic representation of the study design and timeline of events is shown in Figure 4.

HRV analysis: HRV is a marker of VN activity and can be easily measured by software calculating the distance between consecutive R waves on the ECG ³⁷. Importantly, measures of HRV have been inversely correlated with inflammatory cytokines (C-reactive protein, IL-6) in the general population ³⁸⁻⁴⁰. At each visit, a 5-minute ECG will be obtained for HRV analysis. ECG will be obtained in the supine position after resting for 15 minutes while heart rate, blood pressure and respiration will be monitored. All participants will be asked to avoid caffeine for 4 hours and alcohol, smoking and exercise for 12 hours prior to the visit to avoid any interfering with the results of their ECG. This test will done using a PC-Based ECG device. Analysis and interpretation of the HRV data will be performed in a blinded fashion.

Specific Aim 2: To examine the effect of intermittent (1 hour daily) LLTS on inflammatory cytokines and their gene expression in patients with paroxysmal AF over a 6-month period.

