The same group assignment described in Aim 1 will be used for Aim 2. The importance of this Aim is highlighted by accumulating evidence that inflammation promotes the persistence of AF ^{25,41}. Blood samples (10ml) will be collected at baseline and at 3 and 6 months for cytokine measurement. Samples will be centrifuged (4000g for 10 min), and serum will be stored in aliquots at -20°C until assayed. Patients' serum will be saved frozen and processed in batches of 10 to 12. The investigators performing the cytokine assays will be blinded to group assignment. All assays will be run at the [name] Lab at OUHSC. Inflammatory cytokines, including TNFα, and IL-6, will be measured using commercially available immunoassays analyzed on a flow cytometer (multiplex assays). In addition, peripheral blood mononuclear cells (PBMCs) will be isolated using MACS magnetic bead purification. Inflammatory cytokine gene expression profile will be measured at the above time points, using commercially available microarrays. Finally, we will perform exploratory analyses in order to determine relationships between clinical and cytokine responses to LLTS and identify predictors of response based on baseline cytokine levels. It is known that vagus nerve stimulation attenuates inflammation through the cholinergic antiinflammatory pathway ²⁰⁻²⁴. If this pathway is important in AF as well, we expect that the decrease in cytokines will be correlated with the anti-arrhythmic effect.

Duration of participation

Enrolled patients will participate for a maximum of 7 months with 3 outpatient office visits at 1, 3 and 6 months.

Patient enrollment

[figure not shown]
A maximum of 52 patients meeting the inclusion criteria and not meeting the exclusion criteria will be enrolled in the study. The enrollment period is expected to last for at least 17 months, given that on average 30 patients with paroxysmal AF are seen in our clinics each month and assuming that 1 out of 4 eligible patients would agree to participate in the study.

Data collection and analysis

The final data will be pooled and analyzed by the investigators.

E. Statistical methods

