Sample size and power calculations: For purposes of sample size calculations we have simplified the analysis to focus on the AF burden at the 6-month time point between the 2 groups. Assuming a mean±standard deviation AF burden in the control group of $28.4\pm31.2\%$ ³⁴ and a 87% reduction in the LLTS group to 3.7% (assuming a common standard deviation of 31.2%), 26 patients per group would provide 80% power to detect the specified effect sizes at a two-sided significance α level of 0.05. Approximately 30 patients with paroxysmal AF are seen in our clinics each month. Assuming that 1 out of 4 eligible patients would agree to participate in the study, we should be able to enroll the required number of patients within the proposed 17 months, allowing for 6 months of additional follow up and a final month for data analysis.

F. Gender/Minority/Pediatric Inclusion for Research

Participants will be age 21 or older. Race, minority status and gender will not affect enrollment.

[figure not shown]
G. Human participants

The study population will include 52 male/female patients with paroxysmal AF, aged 21 or older, including all races. Since AF is extremely rare in patients less than 21 years old, this age limit is not expected to affect the overall results.

Inclusion Criteria:

- 1. Male and female patients older than 21 year old
- 2. Paroxysmal AF

Exclusion Criteria:

- 1. Left ventricular dysfunction (Left ventricular ejection fraction <40%)
- 2. Significant valvular disorder (i.e., prosthetic valve or hemodynamically relevant valvular diseases)
- 3. Recent (<6 months) stroke or myocardial infarction
- 4. Severe heart failure (NYHA IV)
- 5. Left atrial dilatation (>55mm)
- 6. Recurrent vaso-vagal syncopal episodes
- 7. Unilateral or bilateral vagotomy
- 8. Pregnancy or breast feeding
- 9. Sick sinus syndrome, 2nd or 3rd degree AV block, bifascicular block or prolonged (PR>300ms) 1st degree AV block.
- 2. Identify sources of research material in the form of specimens, records or data.

The research information will consist of the AF burden and serum inflammatory cytokines at each time point specified in the protocol (see Figure 4).

- 3. Describe plans for recruitment and consent procedures to be followed.
- a. Describe the location where consent is most likely to take place (will consent be obtained while an inpatient, in the ER/ICU, will consents be mailed with follow-up meeting to discuss the consent, etc.).

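### Do the two study calendars, and the unstated order of the 6-month patch and visit, leave the primary endpoint window undefined?

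*Combined protocol and SAP*

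**What the plan says.** Four places bear on timing.

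- **Section D, Specific Aim 1, study duration.** Enrolment runs over 17 months, and "the total duration of the study will be 24 months (each patient will be followed for 7 months" is the overall calendar.
- **Section E, sample size paragraph.** Recruitment is argued to be feasible within the same 17 months, "allowing for 6 months of additional follow up and a final month for data analysis".
- **Section D, Duration of participation.** "Enrolled patients will participate for a maximum of 7 months with 3 outpatient office visits at 1, 3 and 6 months".
- **Section D, follow-up visits.** The 3- and 6-month visits include a short ECG and a blood draw. The text then adds: "In addition, patients will undergo noninvasive continuous ECG monitoring for 2 weeks to evaluate their AF burden using an adhesive patch". At every follow-up visit, month 6 included, "the discomfort threshold for tragus stimulation will be obtained to ensure that patients are receiving adequate stimulation". The section then says: "A schematic representation of the study design and timeline of events is shown in Figure 4".

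Only at baseline is the order explicit. The patch is worn first and the visit follows: "During the baseline visit (after the 2 week monitoring period"). Section E names AF burden at 6 months as the primary outcome. It provides for combining the 3- and 6-month data when the group-by-time interaction is not significant.

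**The concern.** The two calendars cannot both hold for patients enrolled after month 16. Seven months of follow-up would carry them into the month that section E sets aside for analysis.

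The 14-day patch sits at that boundary, and no readable sentence fixes its first and last day. The order matters in principle. A patch that ends at the 6-month visit measures AF during assigned stimulation. A patch that starts there might measure it after stimulation has stopped, if stimulation stops at 6 months. The primary outcome would then reflect persistence of the effect, and combining months 3 and 6 could mix two kinds of window. The sample size has little slack: 26 per arm gives just under 80% power by t-test, and no dropout allowance is stated. A faded effect would therefore be costly.

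**Working it through.** **1. The plan's own figures.** 17 + 7 = 24 (section D). 17 + 6 + 1 = 24 (section E). The totals agree; only the last month is used differently.

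For the sample size, the difference is 28.4 − 3.7 = 24.7 points, the SD is 31.2, there are 26 per arm, and the test is two-sided at 0.05. The noncentrality is 24.7 / (31.2 × √(2/26)) = 2.854. With 50 degrees of freedom, power is 79.9%, which reproduces the stated 80%. No calendar figure enters this calculation.

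**2. Time per patient.** 14 days = 14/30.44 = 0.46 month.

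- Patch after the 6-month visit: 0.46 + 6 + 0.46 = 6.92 months.
- Patch ending at the visit: 0.46 + 6 = 6.46 months.

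Both respect the 7-month maximum. The first is closer to the 7 months of follow-up in section D.

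**3. Last data for a patient enrolled at month 17.**

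| 17 months counted to | Patch | Last data (month) | Left to month 24 |
|---|---|---|---|
| consent | after visit | 23.92 | 2.4 days |
| consent | ends at visit | 23.46 | 16.4 days |
| randomisation | after visit | 23.46 | 16.4 days |
| randomisation | ends at visit | 23.00 | 1 month |

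A full analysis month survives in only one of the four cases. Under even accrual (an assumption), 52/17 = 3.06 patients enrol in the final month, so about 3 are affected.

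**4. What the text says about order.**

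- The patch is listed as a further procedure of the 3- and 6-month visits.
- Office visits are limited to months 1, 3 and 6, so none is scheduled two weeks before month 6 at which a patch could be fitted.
- The 6.92-month total fits the stated 7 months.
- The baseline order points the other way, but that patch has to come before randomisation, so it is a weak guide to follow-up.

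The month-3 and month-6 patches share one sentence, so nothing suggests that their order differs.

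**5. How large could a loss be?** Suppose the month-6 window were off stimulation and a fraction f of the effect remained. The documents give no value for f or for the correlations, so both are assumed. All figures use 26 per arm.

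For a comparison at 6 months only, the difference is 24.7f. Without baseline adjustment the SD is 31.2 (50 df). With adjustment it is 31.2 × √(1 − ρ²) (49 df).

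For the baseline-adjusted mean of months 3 and 6, the month-3 window lies within the 6-month stimulation period in either order. The difference is then 24.7 × (1 + f)/2 and the SD is 31.2 × √((1 + ρ)/2 − ρ²). At ρ = 0.5 that SD is 31.2 × √0.5 = 22.06 (49 df).

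| f | 6 months, unadjusted | 6 months, adjusted, ρ = 0.5 | Mean of 3 and 6 months, ρ = 0.5 |
|---|---|---|---|
| 1.00 | 79.9% | 89.8% | 97.7% |
| 0.90 | 71.2% | 82.8% | 96.4% |
| 0.75 | 55.6% | 67.8% | 93.3% |
| 0.50 | 28.8% | 36.6% | 84.3% |

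At f = 0.50, for ρ from 0.3 to 0.7, the adjusted 6-month figure runs from 31% to 50% and the combined figure from 80% to 94%. The combined column ignores the preliminary interaction test. It applies only when months 3 and 6 are in fact combined.

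**The case for a change.** The strongest case for acting is that this window is the primary outcome, that its days are not fixed in any readable sentence, and that two sentences of wording would settle it before anyone sees data. The section E calendar taken literally needs a patch that ends at the visit, while the 7 months in section D is approached only with a patch after it. On that view the plan points in two directions about its main measurement.

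Part of this stands. The mismatch is real, the readable text does not state the order, and a sentence would do no harm.

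The rest does not carry. Section E's sentence argues recruitment feasibility in whole months and defines no measurement window. Elsewhere section D expects enrolment to last at least 17 months, so the calendar is approximate throughout. A half-month difference in such a statement is poor evidence about patch order. The timeline is assigned to Figure 4, whose absence from the extracted text is not an omission in the plan.

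The low power figures depend on an off-stimulation window that no passage states. The discomfort-threshold check at month 6 leaves continued stimulation open. They also depend on assumed fading and on a 6-month-only contrast. Counting logged stimulation days inside each window would use an existing record ("Participants will be requested to keep a daily log with the time and duration of LLTS application"). It would be descriptive only, and might be incomplete in the very case that raises the worry, since the text does not say whether the log continues after the 6-month visit.

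**Conclusion.** The concern does not call for a change to the plan. The calendar difference is a clerical slip. It concerns the last month of a 24-month plan and about 3 patients under even accrual. At most it shortens the time for analysis, and it changes no sample size, power, significance level or estimate.

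The patch order is at most a missing detail that Figure 4 may already supply. The readable text leans toward a patch applied at the visit, and the order is shared by both arms and by both follow-up times. An analyst would take the 14 days of patch recording attached to the 6-month visit as the primary window, and the between-arm comparison would be valid under either order.

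Two limits remain. Figure 4 could not be read. And if stimulation did stop before the patch and the effect faded, a 6-month-only comparison would lose power. That outcome rests on assumptions that the documents neither state nor quantify.
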